## PROTOCOL AMENDMENT SUMMARY OF CHANGES TABLE

DOCUMENT HISTORY						
Document	Date					
Amendment 2	13 May 2022					
Amendment 1	12 May 2021					
Original Protocol	1 April 2021					

# **Amendment 2 (13 May 2022)**

**Overall Rationale for the Amendment:** To ensure exclusion criterion regarding low density lipoprotein (LDL) cutoff value (above which statin therapy should be initiated) is in line with the guidelines for management of dyslipidemia by the European Society of Cardiology.

Section Number and Name	Description of Change	Brief Rationale
Section 5.2	Updated the LDL cutoff-value from 160 mg/dL to	To bring cutoff value in line with
Exclusion Criteria.	>190 mg/dL in Exclusion Criterion 1.	the guidelines for management of
		dyslipidemia by the European
		Society of Cardiology.
Section 3 Objectives	Updated secondary endpoint from "Change from	To ensure consistence with all other
And Endpoints.	baseline in coronary flow reserve (CFR) at Week	endpoints throughout the protocol.
	16 and Week 24 among participants with CFR in	
	the ranges of 2 to 2.49, 2.5 to 3, and 3.01 to 3.5 at	
	baseline" to "Change from baseline in CFR at	
	Week 16 and Week 32 among participants with	
	CFR in the ranges of 2 to 2.49, 2.5 to 3, and 3.01 to	
	3.5 at baseline".	
Throughout the	Minor grammatical, formatting, or spelling changes	Minor errors were noted.
protocol.	were made.	

# **Amendment 1 (12 May 2021)**

**Overall Rationale for the Amendment:** The protocol was amended to include tests and measurements to screen study participants for metabolic syndrome. In addition, the method used for calculation of body surface area (BSA) affected by psoriasis was updated, and the latest versions of the patient reported outcomes (PRO) questionnaires were added to the protocol.

Section Number and Name	Description of Change	Brief Rationale
Schedule of Activities.	
 
Measurement of waistline circumference was added as part of physical examination at Screening Visit S1.
 
The lipid panel was changed to include metabolic tests, and serum glucose and serum insulin tests were added to the panel.
 
	To screen study participants for metabolic syndrome.
Schedule of Activities.	Foot note "g" pertaining to cardiology assessments was updated.	To ensure participant comfort and compliance, participants who have fasted for the lipid and metabolic panel at Weeks 16 and 32 will be permitted to have a non-caffeinated drink prior to the cardiology assessments.
Section 8: Study Assessments and Procedures.	Text in the "Study Visits Weeks 16 and 32" section was updated.	To ensure participant comfort and compliance, participants who have fasted for the lipid and metabolic panel at Weeks 16 and 32 will be

CONFIDENTIAL – FOIA Exemptions Apply in U.S.

Section Number and Name	Description of Change	Brief Rationale				
		permitted to have a non-caffeinated drink prior to the cardiology assessments.				
Section 8.1.2:	The section "Body Surface Area" was	Text consistent with the updated "Rule of 9"				
Psoriasis Assessments.	updated, and a new reference was added.	calculation for BSA measurement was added.				
Section 8.2.1:	Measurement of waistline	To screen study participants for metabolic				
Physical	circumference was added to the list of	syndrome.				
Examination.	physical examinations.					
Section 10.2	The lipid panel was changed to include	To screen study participants for metabolic				
Appendix 2:	metabolic tests, and serum glucose and	syndrome.				
Clinical Laboratory	serum insulin tests were added to the					
Tests.	panel.					
Section 10.7	A new "Appendix 7: Body Surface	The new appendix is consistent with the				
Appendix 7.	Area" was added.	updated "Rule of 9" used for BSA				
		measurement.				
Throughout the	Minor grammatical, formatting, or	Minor errors were noted.				
protocol.	spelling changes were made.					

## 1. PROTOCOL SUMMARY

# 1.1. Synopsis

A Phase 4, Interventional, Single-arm, Open-label Study Evaluating the Effect of Guselkumab on Cardiovascular Risk Surrogate Markers in Participants With Moderate to Severe Plaque Psoriasis

Effect of Guselkumab on Cardiovascular Risk Surrogate Markers in Patients With Moderate to Severe Plaque Psoriasis

Guselkumab is a fully human immunoglobulin G1 lambda monoclonal antibody that binds to the p19 protein subunit of human interleukin 23 (IL-23) with high specificity and affinity. Binding of guselkumab to the IL-23 p19 subunit blocks the binding of extracellular IL-23 to the cell surface IL-23 receptor, inhibiting IL-23 specific intracellular signaling and subsequent activation and cytokine production. Guselkumab is indicated for the treatment of moderate-to-severe plaque psoriasis in adults who are candidates for systemic therapy. However, there may be potential benefits for guselkumab beyond those related to skin clearance. The promising results of IL-12/23 inhibition in the Vascular Inflammation in Psoriasis-Ustekinumab (VIP-U) study, combined with the role of IL-23 in the early stages of atherogenesis, suggest a potential benefit of IL-23 inhibition on vascular inflammation. This study aims to investigate the effect of guselkumab on surrogate markers of cardiovascular risk in participants with moderate-to-severe plaque psoriasis.

### **OBJECTIVES AND ENDPOINTS**

Objectives	Endpoints					
Primary						
To evaluate the effect of guselkumab on CFR measured by transthoracic doppler-echocardiography, in participants with moderate-to-severe psoriasis and intermediate cardiovascular risk*.	• Change from baseline † in CFR at Week 32.					
Secondary						
To evaluate the short-term effect of guselkumab on CFR measured by transthoracic doppler-echocardiography, in participants with moderate-to-severe psoriasis and intermediate cardiovascular risk.	Change from baseline in CFR at Week 16.					
To evaluate the effect of guselkumab on GLS as	
 
Change from baseline in GLS at Week 32.
 
					
a surrogate marker of left ventricular function in participants with moderate-to-severe psoriasis and intermediate cardiovascular risk.	Change from baseline in GLS at Week 16.					
To evaluate the effect of guselkumab on arterial	
 
Change from baseline in cfPWV at Week 32.
 
					
stiffness in participants with moderate-to-severe psoriasis and intermediate cardiovascular risk.	• Change from baseline in cfPWV at Week 16.					
To evaluate the effect of guselkumab on CFR among participants in the different CFR categories.	• Change from baseline in CFR at Week 16 and Week 32 among participants with CFR in the ranges of 2 to 2.49, 2.5 to 3, and 3.01 to 3.5 at baseline.					
To evaluate the effect of guselkumab on surrogate CV risk markers among nicotine users and non-users in the participant population.	
 
Change from baseline in CFR at Week 16 and Week 32 among nicotine users and non-users.
 
Change from baseline in GLS at Week 16 and Week 32 among nicotine users and non-users.
 
Change from baseline in cfPWV at Week 16 and Week 32 in nicotine users and non-users.
 
					

CONFIDENTIAL – FOIA Exemptions Apply in U.S.

Objectives	Endpoints
To assess the safety and tolerability of	Rate of AEs among participants treated with guselkumab.
guselkumab in participants with moderate-to-	
severe plaque psoriasis and intermediate	
cardiovascular risk.	

\*Intermediate cardiovascular risk defined by CFR ≥2 and ≤3.5 at Screening Visit S2.

t cfPWV, GLS and CFR measurements at Week 0 will be considered as the baseline value. CFR must not be <2 or >3.5 at both Screening Visit S2 and Week 0.

**Abbreviations:** AE= Adverse event; cfPWV = carotid-femoral pulse wave velocity; CFR= Coronary Flow Reserve; GLS: Global Longitudinal Strain

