#### OVERALL DESIGN

This is an interventional, single-arm, open-label, oligocentric study to evaluate the effect of guselkumab on cardiovascular risk surrogate markers in adult men and women diagnosed with moderate-to-severe plaque psoriasis (with or without PsA) for at least 6 months prior to study entry. Eligibility of the participants will be assessed at 2 screening visits; at Screening Visit S1, participants will be screened at the dermatology department based on skin assessments, medical history, and laboratory parameters. Participants fulfilling eligibility criteria at Screening Visit S1 will be referred to the cardiology department, and will undergo cardiologic assessments (GLS, CFR [via transthoracic doppler echocardiography] and cfPWV) at Screening Visit S2, and again at Week 0. Only participants with CFR ≥2 and ≤3.5 at both these time-points will be enrolled in the study. The CFR measurement at Week 0 will be considered as the baseline value.

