Key efficacy evaluations will be carried out at the time-points detailed in the Schedule of Activities, and will include cardiology assessments (cfPWV, GLS and CFR), and skin assessments (IGA, PASI and BSA). Efficacy assessments will be done locally at the sites. The CFR assessments for eligibility will be immediately evaluated on-site at Screening Visit S2 and Week 0. All the CFR and GLS assessments in the study will be reviewed by a cardiology core lab for blinded analysis of endpoints. Quality-of-life and lifestyle changes during the study will be measured using the Dermatology Life Quality Index (DLQI), Pittsburg Sleep Quality Index (PSQI) and Alcohol Use Disorders Identification Test (AUDIT) questionnaires, and mood and anxiety will be assessed using the Hospital Anxiety and Depression Scale (HADS, if available).

Safety evaluations will include monitoring of vital signs, 12-lead electrocardiogram (ECG) at Screening Visit S1, monitoring of tuberculosis status, pregnancy testing at each visit, and recording of AEs throughout the study. Biomarker assessments will include the evaluation of relevant markers in serum, plasma, and urine for all participants.

For participants completing the study, the total duration will be 40 weeks, including 28 weeks of treatment and a Final Efficacy Visit 4 weeks later (Week 32). The Final Safety Visit will occur 12 weeks after the last dose of the guselkumab (Week 40). Participants who discontinue guselkumab prior to Week 28 will be considered to have completed the study if they complete all the assessments of the Final Efficacy Visit at the time of discontinuation (or soon after), and the Final Safety Visit scheduled 12 weeks after the last guselkumab dose. For participants who opt to receive commercially available guselkumab from their healthcare provider after Week 28, the visit at which the first dose of guselkumab is received outside the study (Week 36) will be considered as the Final Safety Visit.

An interim analysis will be conducted after a sufficient proportion of the participants (to be defined during the study) have accrued Week 16 CFR measurements. The scope of the interim analysis will be developed and documented in a statistical analysis plan.

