## Participant population-related inclusion criteria

The participant

- 1. Is male or female (according to their reproductive organs and functions assigned by chromosomal complement), 18 years of age (or the legal age of consent in the jurisdiction in which the study is taking place) and above.
- 2. Has a diagnosis of moderate-to-severe plaque psoriasis (with or without PsA) for at least 6 months prior to the first dose of guselkumab at Week 0. Moderate-to-severe plaque psoriasis is defined as PASI≥12, IGA≥3 and involved BSA≥10% at Screening Visit S1. Participants with a predominantly non-plaque form of psoriasis (eg, erythrodermic, guttate, or pustular) will not be eligible for inclusion in the study.
- 3. Has intermediate cardiovascular risk defined by CFR  $\geq 2$  to  $\leq 3.5$  (Criterion to be assessed by cardiologist at Screening Visit S2 and Week 0).

- 4. Is a candidate for systemic treatment for psoriasis (either naïve or history of previous treatment).
- 5. Does not have any abnormalities in physical examination, medical history, clinical laboratory tests, vital signs, and 12-lead ECG performed at screening that are not consistent with the underlying illness in the study population. This determination must be recorded in the participant's source documents and initialed by the investigator. The 12-lead ECG must be assessed by the dermatologist at Screening Visit S1.
- 6. Must sign an informed consent form (ICF) indicating that he or she understands the purpose of, and procedures required for, the study and is willing to participate in the study.

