#### 9.2. Sample Size Determination

The sample size calculation is based on the assumption that participants will show an average increase of 20% in CFR at Week 32. To detect a CFR mean change of 0.3 from baseline with 80% power, and assuming a SD of 0.8 and a 5% dropout rate, 50 participants are expected to be enrolled in the study.

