5. STATISTICAL ANALYSES

5.1. General Considerations

Descriptive statistics (eg, mean, median, standard deviation (SD), minimum, and maximum) will be used to summarize continuous variables. Counts and percentages will be used to summarize categorical variables. Graphic data displays may also be used to summarize the data. In addition, graphical data displays (eg, line plots) and participant listings may also be used to summarize the data.

The summarized data will be presented by Nicotine-user, non-Nicotine user and total group.

Baseline Value: For all endpoints the last non-missing measurement prior to or on the day of the first administration of the study treatment (guselkumab) will be the Baseline value in the study (i.e., at 'Week 0, Baseline' analysis visit, following assignment of the actual visits using visit windows, as indicated in Table 2).

Level of Significance: In general, all tests will be performed at a 2-sided significance level of 0.05, unless otherwise specified. All interval estimations will be reported using 2-sided 95%CI. Nominal p-values will be presented.

Change from Baseline:

For the continuous variables pertaining to the cardiology outcomes, skin related outcomes, or paper PRO outcomes the determination of change from baseline will be determined only when both, baseline and the measurement for the particular visit is available.

Change from Baseline at visit x = Measurement from the visit x - Baseline value of the parmeter

The number of patients with missing change from baseline values will be also presented in the statistical outputs.

For continuous or ordinal efficacy endpoints, a Mixed-effect Model for Repeated Measures (MMRM) will be used. Covariates such as Nicotine use, body mass index (BMI), presence, or absence of PsA, age, gender, and visit will be incorporated into these models.

For binary efficacy endpoints, 95% confidence interval [CI] for binomial proportions will be provided using exact methods, such as Clopper-Pearson or Chan-Zhang.

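### Baseline for CFR, GLS and cfPWV uses the Week 0 visit alone: SAP Table 2 shuts out the pre-dose S2 value even as a fallback, and a modest gain in precision goes unused

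*Protocol*

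**What the plan says.** The protocol synopsis (Overall Design) has the cardiology assessments performed "at Screening Visit S2, and again at Week 0". The Schedule of Activities marks cfPWV, GLS and CFR at both visits, 2 to 4 weeks apart. Both CFR readings count for entry; Inclusion Criterion 3 (CFR 2 to 3.5) carries the note "Criterion to be assessed by cardiologist at Screening Visit S2 and Week 0".

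Only one visit supplies the baseline: "cfPWV, GLS and CFR measurements at Week 0 will be considered as the baseline value" (objectives table footnote) and "The CFR measurement at Week 0 will be considered as the baseline value" (Overall Design). Eligibility rests on the site reading (Protocol 8.1), but under Protocol 4.1 "All the CFR and GLS assessments in the study will be reviewed by a cardiology core lab for blinded analysis of endpoints".

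SAP 5.1 sets baseline as the latest available value up to the day of first dose, and links this to the Week 0 analysis visit of Table 2. That table gives Day -13 to 1 for CFR, GLS and cfPWV, and Day -27 to -14 for the S2 cardiology readings. SAP 5.1 adds that "the determination of change from baseline will be determined only when both, baseline and the measurement for the particular visit is available". The primary model (SAP 5.3.3.1) uses the Week 0 CFR as its baseline covariate. S2 values reappear only in SAP 5.7.7, which plans an S2 versus Week 0 analysis of all three measures.

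**The concern.** Two consequences follow.

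First, the SAP's rule and its window disagree. Taken literally, the rule in 5.1 would fall back to S2 when the Week 0 value is absent; Table 2 does not allow that. With no baseline there is no change score.

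Second, in a single-arm study the precision of the mean change depends on the SD of the change score, and a one-visit baseline carries the full visit-to-visit variation into that SD. A second pre-dose assessment has been collected, sent to the core lab (CFR and GLS) and scheduled for analysis, yet it adds nothing to the estimate. The study closed early with few participants, so more enrolment cannot make up the difference.

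**Working it through.** **Plan's own figure.** Protocol 9.2: "To detect a CFR mean change of 0.3 from baseline with 80% power, and assuming a SD of 0.8 and a 5% dropout rate", giving 50 enrolled. The level is stated in SAP 5.1: "In general, all tests will be performed at a 2-sided significance level of 0.05, unless otherwise specified". Treating 0.8 as the SD of the change (the documents do not say which SD it is):

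- Normal formula, two-sided: n = (0.8 × (1.960 + 0.842) / 0.3)² = 55.8, so 56 evaluable; 56 / 0.95 gives 59 enrolled.
- Exact t, two-sided: 58 evaluable, 62 enrolled.
- Exact t, one-sided 5%: 46 evaluable, 49 enrolled.

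So 50 is not reproduced at the stated two-sided level. That is a separate matter. Here I take 50 × 0.95, about 47 completers, where two-sided t power is 71%.

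**Effect of averaging.** Let w be the visit-to-visit variance and t the variance between people in true change.

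- Baseline from one visit: Var(change) = 2w + t.
- Baseline from the mean of two visits: Var(change) = 1.5w + t.
- Proportional cut = 0.5w / (2w + t). It is largest, 25%, when t = 0.

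With r the S2–Week 0 correlation, ρ the Week 0–Week 32 correlation and equal visit variances, the variance ratio is 1 − (1 − r) / (4(1 − ρ)). Neither correlation is in the documents, so these are assumed values:

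| r | ρ | Variance ratio | SD of change | Power, n = 47 |
|---|---|---|---|---|
| (Week 0 only) | | 1.00 | 0.800 | 71% |
| 0.5 | 0.5 | 0.75 | 0.693 | 83% |
| 0.8 | 0.7 | 0.833 | 0.730 | 79% |
| 0.8 | 0.5 | 0.90 | 0.759 | 76% |
| 0.9 | 0.5 | 0.95 | 0.780 | 73% |

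**With the entry gate.** Simulation with CFR held to 2–3.5 at both S2 and Week 0, assuming mean CFR 2.6–3.0, between-person SD 0.3–0.6 and visit SD 0.3–0.5:

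- Identical response in everyone: variance of change falls about 14–22%, but its SD is then only 0.40–0.64.
- Response variation added (SD about 0.5–0.7) until the SD of change is near 0.8: the cut is about 6–9% (5–10% at the extremes). SD falls to 0.8 × √0.94 = 0.776 or 0.8 × √0.91 = 0.763, and power is about 74% or 75%. At a 5% cut it is 73%.
- Residual variance after adjusting for baseline: down about 2–14% in the first case and 1–4% in the second.
- Mean drift with no drug effect: the same for both baselines to within 0.001, because both readings pass the same gate.

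The documents give no SD for GLS or cfPWV, so their gain cannot be sized.

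**Who loses a change score.** For CFR, the Schedule of Activities (footnote g) withholds the first dose until a CFR is obtained and allows repeat attempts. The remaining gap is a scan accepted on site but unreadable at the core lab. For GLS the same gap exists, and neither GLS nor cfPWV has a rule holding the dose until a value is obtained. In each case the participant has been dosed and stays in the FAS (SAP 4) without that endpoint's change score.

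**The case against.** A Week 0 baseline, the last assessment before dosing, is standard, valid and stated consistently. That stands: this is an efficiency point plus an inconsistency in the SAP.

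A reader might infer more than the documents support:

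- That a participant with a failed Week 0 scan drops out. For CFR, dosing waits for a successful scan, and a Week 0 CFR in range is itself an entry condition. For the other measures, only one endpoint's change is lost.
- That each baseline is a single reading. SAP 5.4.1.1.2 averages triplicate cfPWV readings. That does not remove variation between visits, so the point concerns one visit.
- That S2 is discarded. It decides eligibility and is analysed under SAP 5.7.7.
- That power would reach 83%. This needs all of the 0.8 SD to be visit noise, a visit SD of 0.8 / √2 = 0.566, above the assumed range.
- That averaging cures regression to the mean from the entry gate. It does not.

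Two further objections carry weight. S2, at Day -27 to -14, lies inside the 4-week washout of Exclusions 22–23, so carry-over from earlier therapy could affect it. And the SAP (21 July 2023) post-dates termination (31 May 2023) in an open-label study, so replacing the protocol's primary baseline now would be a post hoc change. Both argue for keeping Week 0 and reporting the averaged analysis beside it.

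The planned baseline-adjusted MMRM also narrows the visible gain, since its reported intervals depend on residual variance. But adjustment does not reduce the true sampling variance of the overall mean change: with complete data, the LS mean at the average baseline is the raw mean change. How the core lab handles unreadable scans may be set out in process documents not available here.

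**Conclusion.** The point holds as a cheap improvement. Table 2 conflicts with the rule in SAP 5.1 and denies a change score to any dosed participant who has an S2 value but no usable Week 0 value; how many that affects cannot be told from the documents. The precision left unused is modest: at most 25% of change-score variance, about 14–22% with little variation in response, and about 6–9% if the SD of change is near 0.8. The last is equivalent to 6–10% more participants (1/0.94 to 1/0.91), with power rising from about 71% to roughly 73–75%. Model residual variance falls by roughly 1–14%. These sizes rest on equal variance at each visit, on correlations and SDs that I assumed, and on reading 0.8 as the SD of change. SAP 3 sets the original sample-size calculation aside after termination, so the power figures describe the original plan; the effect on interval width still applies.

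**What to change.** Make both changes without reference to outcome data:

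1. In SAP 5.1 and Table 2, let the S2 value serve as baseline for CFR, GLS and cfPWV when the Week 0 value is missing or unreadable at the core lab. This brings the window into line with the SAP's own rule.
2. Pre-specify an analysis of change from the mean of S2 and Week 0, using core-lab readings for CFR and GLS, with that mean also as the MMRM covariate. Report it alongside the Week 0-only analysis, and state which baseline defines the CFR categories.

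Eligibility stays as it is. The cost is SAP wording and a few lines of programming, with no new scans or reads. The named downside is possible carry-over at S2 from therapy stopped for the washout; comparison with the Week 0-only analysis shows whether it matters.

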### **Hypothesis**

The primary hypothesis of this study is that guselkumab (administered as 100 mg at Weeks 0, 4, 12, 20 and 28) is effective in reducing surrogate markers of cardiovascular risk as assessed by the change from baseline in CFR at Week 32.

#### OVERALL DESIGN

This is an interventional, single-arm, open-label, oligocentric study to evaluate the effect of guselkumab on cardiovascular risk surrogate markers in adult men and women diagnosed with moderate-to-severe plaque psoriasis (with or without PsA) for at least 6 months prior to study entry. Eligibility of the participants will be assessed at 2 screening visits; at Screening Visit S1, participants will be screened at the dermatology department based on skin assessments, medical history, and laboratory parameters. Participants fulfilling eligibility criteria at Screening Visit S1 will be referred to the cardiology department, and will undergo cardiologic assessments (GLS, CFR [via transthoracic doppler echocardiography] and cfPWV) at Screening Visit S2, and again at Week 0. Only participants with CFR ≥2 and ≤3.5 at both these time-points will be enrolled in the study. The CFR measurement at Week 0 will be considered as the baseline value.

